9.2. Setting

This study will use the US-based Optum's deidentified EHR data, with supplemental linkage to Optum's Integrated Claims-Clinical adjudicated claims dataset for those patients in the EHR who also have claims data available. For a subset of patients in the EHR, data exist including patient electronic clinical notes which will allow manual clinician review at Optum to confirm clinical diagnosis of ATTRwt-CM or non-amyloid heart failure based on available data that align with the Pfizer clinician specified specification. Optum's role, processes, and data is described in more detail in [Section 9.4](#) and [Section 9.6](#).

9.2.1. Inclusion Criteria

Primary Analysis

This study will include HF patients (defined as having ≥ 1 claim for HF or HF treatment) ≥ 50 years old with clinical diagnosis of ATTRwt-CM or non-amyloid HF ascertained by charts. Patients will be required to have ≥ 12 months of continuous activity in the EHR or claims prior to the Index Date.

Sensitivity analysis (pending feasibility assessment)

1. The earliest HF diagnosis or treatment date as the index date
2. Patients without HF diagnosis or treatment (pending feasibility assessment)
3. High Risk Population:

PFIZER CONFIDENTIAL

CT24-WI-GL02-RF02 4.0 Non-Interventional Study Protocol Template For Secondary Data Collection Study

01-Jun-2022

Page 15 of 25

- Age 65+
- Male gender
- Presence of carpal tunnel syndrome

9.2.2. Exclusion Criteria

Patients with any of the following diagnoses:

- Light chain (AL) amyloidosis
- Intracranial hemorrhage
- Cerebral amyloid angiopathy
- End stage renal disease
- Blood cancer

9.3. Derived Variables

Variable	Role	Operational definition
HF	Index	
• Latest claim/encounter for HF or HF treatment (see Appendix B for the code list)
ATTRwt-CM	Exposure	
• Confirmed: Ground truth ascertained by charts• Suspected ATTRwt-CM: Identified by the ML algorithm (predicted probability ≥ 0.5)• Not Suspected with ATTRwt-CM/non-amyloid heart failure: Identified by the ML algorithm (predicted probability < 0.5)

9.4. Data Sources

Optum's EHR and Integrated Claims-Clinical dataset, which combines adjudicated claims data (where available) with Optum's EHR data, are the data sources for this study. Optum integrates EHR data with claims, prescribing, dispensing, and practice management data by partnering directly with several multi-specialty medical groups, IDNs and hospital chains to extract data from their EHR and various information technology systems in the US. By normalizing, validating, and aggregating the de-identified data, Optum generates a longitudinal view of patient care.

Optum's longitudinal EHR repository is derived from dozens of healthcare provider organizations in the US, that include more than 57 contributing sources and 111K sites of care: treating more than 106 million patients receiving care in the US. The data is certified as de-identified by an independent statistical expert following HIPAA statistical de-identification rules and managed according to Optum customer data use

agreement.^{1,2} Clinical, claims and other medical administrative data is obtained from both Inpatient and Ambulatory EHRs, practice management systems and numerous other internal systems. Information is processed, normalized, and standardized across the continuum of care from both acute inpatient stays and outpatient visits. Optum data elements include demographics, medications prescribed and administered, immunizations, allergies, lab results (including microbiology), vital signs and other observable measurements, clinical and inpatient stay administrative data and coded diagnoses and procedures. In addition, Optum uses natural language processing (NLP) computing technology to transform critical facts from physician notes into usable datasets. The NLP data provides detailed information regarding signs and symptoms, family history, disease related scores (ie, RAPID3 for RA, or CHADS2 for stroke risk), genetic testing, medication changes, and physician rationale behind prescribing decisions that might never be recorded in the EHR.

Diagnosis data, laboratory data, and surgical procedure data for the study period of interest will be first be obtained from structured data (via International Classification of Diseases, Ninth Revision/Tenth Revision, Clinical Modification [ICD-9-CM/ICD-10-CM], International Classification of Diseases, Ninth Revision/Tenth Revision, Procedure Classification System [ICD-9- PCS/ICD-10-PCS], or Current Procedure Terminology (CPT) codes where applicable. Drug treatment data may also be pulled from prescription written, medication administration, and procedure tables when appropriate (via ICD-9-CM/ICD-10-CM, National Drug Center [NDC], CPT, and Healthcare Common Procedure Coding System [HCPCS] codes where applicable). In addition, Optum will use data available in the medical records for a subset of patients with heart failure that have clinical patient notes and other data that cannot be mapped into the larger structured database. These data may contain verbatim medical data, including text-based descriptions of medical information, such as medical records, physician notes, neurological scans, X-rays, or narrative fields in a database. When possible/appropriate, for validation of ATTRwt-CM or nonamyloid heart failure diagnoses and analyses of risk factors and background epidemiology, lab data will also be used to augment the structured electronic health data.

9.5. Study size

The sample size formula follows the binomial approach for binary outcomes where:

$$N^{0.5} = (Z_{1-\alpha} + Z_{1-\beta}) (p(1-p))^{0.5} / M$$

For 90% power, the formula results in 78 individuals for sensitivity and 128 individuals for specificity. Using various keyword search, feasibility assessment was performed. In the Optum EHR data, after applying inclusion and exclusion criteria in [Section 9.2.1](#) and [Section 9.2.2](#), there were 422 potential ATTRwt-CM records available; yet, before reviewing the unstructured notes, one is unable to determine the total number of clinically diagnosed ATTRwt-CM patients. Given that ATTRwt-CM is a rare disease for which the ICD-10 code has only been available recently and the use of which clinicians are still not quite familiar with or comfortable using, the team will attempt to maximize the number of

PFIZER CONFIDENTIAL

potential cases by performing note review for all 422 charts. Similar number of control charts will be reviewed to balance the number of cases and controls. Any increase in sample size will result in more precise 95% CIs.

We estimate that the sample sizes will likely provide 90% power to satisfy the non-inferiority hypotheses listed below.

The non-inferiority hypotheses are:

H0: Sensitivity ≤ 0.80

H1: Sensitivity ≥ 0.90

and

H0: Specificity ≤ 0.72

H1: Specificity ≥ 0.82

Sensitivity and Specificity estimates were evaluated based on the validation and performance metrics from the random forest-based ML risk prediction model receiver operating characteristics curve in Huda et al.¹ Sensitivity is defined as the probability that an individual with the disease in the population will screen positive for disease by the algorithm (True Positives). Specificity is defined as the probability that an individual without the disease will be correctly identified as not having the disease by the algorithm (True Negatives).

The distance from H0 to H1 is the non-inferiority margin (NIM), which is 0.10 for both sensitivity and specificity.

For sensitivity, we wish to reject H0 (inferiority to 0.90) in favor of H1 (non-inferiority to 0.90) while for specificity we wish to reject H0 (inferiority to 0.82) in favor of H1 (non-inferiority to 0.82).

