Data source: Optum's Electronic Health Record and Integrated Claims-Clinical database that combines adjudicated claims data (where available) with Optum's EHR data, are the data sources for this study. In addition, this study will use data available in the unstructured for a subset of ATTRwt-CM and non-amyloid heart failure among patients with HF that have clinical patient notes and other data that cannot be mapped into the larger structured database. Optum's longitudinal repository is derived from dozens of healthcare provider organizations in the US, that include more than 57 contributing sources and 111K sites of care: treating more than 106 million patients receiving care in the US.

Sample size: Using various keyword search, feasibility assessment was performed. In the Optum EHR data, there were 422 potential ATTRwt-CM records available; yet, before reviewing the unstructured notes, one is unable to determine the total number of clinically diagnosed ATTRwt-CM patients. Given that ATTRwt-CM is a rare disease, the team will attempt to maximize the number of potential cases by performing note review for all 422 charts. Similar number of control charts will be reviewed to balance the number of cases and controls. We estimate that the sample sizes will likely provide 90% power to satisfy the non-inferiority hypotheses.

Data analysis: The ML model will identify patients with HF as suspected ATTRwt-CM and the remainder patients as not suspected for ATTRwt-CM/non-amyloid heart failure. The patients with HF will be entered in the ML algorithm along with their diagnosis codes listed in all their records. The model will classify patients based on the presence and absence of cardiac and non-cardiac features and categorized as suspected (at-risk) or not suspected with ATTRwt-CM. The model performance metrics (sensitivity and specificity) will be calculated based on the concordance between case ascertainment of ATTRwt-CM using diagnostic codes with ascertainment using clinical patient notes review, the latter using a variety of criteria to define ATTRwt-CM.

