9.7. Data Analysis

9.7.1. Statistical Methods

The ML model will identify patients with HF as suspected ATTRwt-CM and the remainder patients as not suspected for ATTRwt-CM/non-amyloid HF. The patients with HF will be entered in the ML algorithm along with their diagnosis codes listed in all their records. The model will classify patients based on the presence and absence of cardiomyopathy features and categorized as suspected (at-risk) or not suspected with ATTRwt-CM. The model performance metrics (sensitivity and specificity) will be calculated by cross-tabulating between diagnosis based on ML algorithm and diagnosis based on chart ascertainment.

The analyses for noninferiority of sensitivity and specificity are straightforward. The calculations for these measures are shown below.

PFIZER CONFIDENTIAL

CT24-WI-GL02-RF02 4.0 Non-Interventional Study Protocol Template For Secondary Data Collection Study

01-Jun-2022

Page 19 of 25

Table 1. Sensitivity and Specificity

ML classification	Cohort (Ascertained by Charts)		TP+FP
	ATTRwt-CM	Non-amyloid HF	
+	True Positive (TP)	False Positive (FP)	TP+FP
-	False Negative (FN)	True Negative (TN)	TN+FN
	TP+FN	TN+FP	

Sensitivity = TP / (TP + FN)

Specificity = TN / (TN + FP)

We would then calculate the one-sided 95% confidence interval (CI) for sensitivity, assuming 90% power:

$$95\% \text{ CI} = \text{sensitivity} - 1.645(\text{SE}_{\text{sensitivity}})$$

where $\text{SE}_{\text{sensitivity}} = \text{square root} [\text{sensitivity} - (1-\text{sensitivity})]/n_{\text{sensitivity}}$

The 95% CI for sensitivity must equal or exceed a cut point (CP) value between 0.80 and 0.90 where:

$$\text{CP} = 0.90 - \text{NIM Z1-} \beta / (\text{Z1-}\alpha + \text{Z1-}\beta)$$

When $\alpha = 0.05$ and power = 0.90 we reject inferiority for all values $\geq \text{CP} = 0.8561$.

Similarly, for specificity, we reject inferiority for all values $\geq \text{CP} = 0.7761$.

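### Section 9.7.1 applies the point-estimate cut point to the lower confidence bound, so the 90% power statement fails under that rule; fix the rule and state joint power by confirmed cases and controls

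*Combined protocol and SAP*

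**What the plan says.** Section 9.5 tests sensitivity (null 0.80, alternative 0.90) and specificity (null 0.72, alternative 0.82), joined by the word 'and', with a margin of 0.10 for each. On size it says "For 90% power, the formula results in 78 individuals for sensitivity and 128 individuals for specificity". It plans to review all 422 potential case charts, but "before reviewing the unstructured notes, one is unable to determine the total number of clinically diagnosed ATTRwt-CM patients". For controls, "Similar number of control charts will be reviewed to balance the number of cases and controls". It then concludes "We estimate that the sample sizes will likely provide 90% power to satisfy the non-inferiority hypotheses listed below", and the abstract repeats this: "We estimate that the sample sizes will likely provide 90% power to satisfy the non-inferiority hypotheses". No confirmation yield, joint power or explicit both-must-succeed rule is given.

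Section 9.7.1 sets the decision rule. It begins "We would then calculate the one-sided 95% confidence interval (CI) for sensitivity, assuming 90% power", defines the bound as the estimate minus 1.645 SE, and continues "The 95% CI for sensitivity must equal or exceed a cut point (CP) value between 0.80 and 0.90 where". The cut points are 0.8561 for sensitivity and 0.7761 for specificity. It then describes rejection in terms of values at or above the cut point, without saying whether a value is the bound or the estimate. Specificity follows the same pattern: "Similarly, for specificity, we reject inferiority for all values" at or above 0.7761.

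**The concern.** A lower bound is normally compared with the null value, here 0.80 or 0.72. A cut point lying between null and alternative is normally a threshold for the estimate itself. Section 9.7.1 pairs the bound with the estimate's threshold, which is a much harder test than the one 9.5 sized. Separately, 78 and 128 each target 90% for one endpoint, while the power sentence speaks of the hypotheses in the plural.

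The study exists to test prespecified thresholds, and this is its only power statement. If the rule can be read in more than one way, passing or failing could turn on an interpretation made after the data are seen.

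**Working it through.** **Inputs.** From 9.5 and 9.7.1: one-sided alpha 0.05 (z = 1.645), power 0.90 (z = 1.282), margin 0.10, nulls 0.80/0.72, alternatives 0.90/0.82. Assumptions: true values equal the alternatives; cases and controls are different patients, so joint power is the product of the two powers; the SE is sqrt[p(1−p)/n]. The printed SE shows a minus sign where the product belongs, which is probably a typing slip.

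**Step 1: the plan's own figures.** N = (1.645 + 1.282)² p(1−p) / 0.10².
- Sensitivity, p = 0.90: 77.07, so 78 (78 stated).
- Specificity, p = 0.82: 126.40, so 127 (128 stated; the difference is immaterial).
- Cut point = alternative − 0.10 × 1.282/(1.645 + 1.282) = 0.8562 and 0.7762 (0.8561 and 0.7761 stated).

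**Step 2: what the cut point is.** The same number can be built up from the null: 0.80 + 0.10 × 1.645/(1.645 + 1.282) = 0.8562. So it is the null plus 1.645 SE at the formula's N. Subtracting a further 1.645 SE from the estimate before comparing it with the cut point applies the allowance twice.

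For example, 70 of 78 correct is 0.897, with SE 0.0344 and lower bound 0.841. The bound clears 0.80 but fails 0.8561. At 71 of 78 the bound is 0.857 and passes.

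**Step 3: exact binomial power under each rule.** Find the smallest passing count, then take the binomial upper tail at 0.90 or 0.82.

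| Rule | Counts needed at 78 / 128 | Power, each | Joint, 78/128 | Joint, 78/422 | Joint, 422/422 |
|---|---|---|---|---|---|
| Wald bound ≥ cut point | 71 / 107 | 0.475, 0.370 | 17.6% | 36.1% | 67.0% |
| Point estimate ≥ cut point | 67 / 100 | 0.913, 0.893 | 81.6% | 90.3% | 98.7% |
| Wald bound > 0.80/0.72 | 68 / 100 | 0.846, 0.893 | 75.6% | 84.6% | over 99.9% |
| Exact bound > 0.80/0.72 | 69 / 101 | 0.749, 0.848 | 63.5% | 74.9% | 99.9% |

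For the first rule at 422/422, joint power is 0.880 × 0.761 = 0.670. The best over 20 to 422 per group is 0.899 (416 cases) × 0.761 (422 controls) = 0.684. The result depends on the true values: at 0.92/0.84 and 422/422 it would be 96%.

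If the 9.5 formula held exactly, joint power at its own sizes would be 0.90 × 0.90 = 0.81.

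**Step 4: type I error.** With a fixed cut point on the estimate, the error for sensitivity at a true 0.80 is 12.0% at 78 cases, 3.7% at 150 and 1.8% at 200. For specificity it is 7.2% at 128 controls. The Wald bound against 0.80/0.72 has 6.9% and 7.2% at 78/128; the exact bound has 3.6% and 4.7%.

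**Step 5: joint power by yield, bound against 0.80/0.72, with 422 confirmed controls.**

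| Confirmed cases | Wald | Exact |
|---|---|---|
| 78 | 84.6% | 74.9% |
| 100 | 92.7% | 87.6% |
| 150 | 97.4% | 95.5% |
| 200 | 99.4% | 99.0% |

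Joint power stays at or above 90% from 99 cases (Wald) or 124 (exact), which is 99/422 = 23% or 124/422 = 29% of the case charts. With 211 confirmed controls, an illustrative half yield, the figures are 117 and 147 cases. With only 128 confirmed controls, specificity power alone is 0.893 (Wald) or 0.848 (exact), so joint power cannot reach 90% however many cases are confirmed.

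**The case against.** The strongest reply is that the sponsor meant the point estimate. The closing sentences of 9.7.1 allow that, and 9.5 and 9.7.1 then agree algebraically. With 422 controls, joint power on that reading stays at or above 90% from 105 cases, so the power statement is reasonable at moderate yield. This stands as a possible reading. It does not remove the problem: the preceding sentence makes the confidence limit the quantity that must reach the cut point, so 9.7.1 still holds two rules, and the fixed cut point does not keep alpha at 5% when the number of cases departs from plan.

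A second reply is that 78 and 128 are formula results, not the planned size, and that the sentence is hedged with 'likely'. This also stands. A reader might infer from the 78/128 figures that the study is underpowered or that the 90% is false outright. The documents do not support either inference. All 422 case charts and a similar number of control charts are to be reviewed, and against 0.80/0.72 about 200 confirmed cases with 422 confirmed controls would give 99%. Nor is the sample-size arithmetic wrong, since it reproduces within one.

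Third, 9.5 never says outright that both hypotheses must be rejected. The 'and' implies it, but it is for the sponsor to state. Finally, replacing the Wald bound with an exact one is a preference, not the correction of an error.

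**Conclusion.** The concern holds as an inconsistent decision rule with an unsupported power statement.

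- Under the bound-against-cut-point wording, the 90% does not hold at any yield up to 422 per group: joint power is at most 68%. At the plan's own true values, the algorithm would fail about one time in three even with every chart confirmed.
- Under the point-estimate reading, the 90% is attainable, but type I error drifts with the number of cases, from 12% at 78 to 1.8% at 200.
- Under a bound against 0.80/0.72, the 90% depends on how many cases and controls are confirmed. The plan gives no figure for this, so the statement is unsupported rather than refuted.

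These conclusions rest on true values of 0.90/0.82, both endpoints being required, and the SE read in its usual form. The change should be made before the algorithm is run against the chart results.

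**What to change.** 1. In 9.7.1, delete the cut-point requirement and reject inferiority when the one-sided 95% lower bound exceeds 0.80 for sensitivity and 0.72 for specificity. If the Wald bound is kept, correct the SE to sqrt[p(1−p)/n] and state its type I error (about 7% at 78/128). An exact Clopper-Pearson bound is an option: it keeps type I error at or below 5%, at a cost of about 10 points of power at 78 cases.
2. State in 9.5 and 9.7.1 whether both hypotheses must be rejected, and label 78 and 128 as per-endpoint formula minimums.
3. In 9.5 and the abstract, replace the 90% sentences with joint power by confirmed cases and controls for the chosen bound, using the step 5 figures. Include the lower-control results (211 and 128), because a similar number of control charts reviewed does not guarantee 422 confirmed controls.

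The cost is wording in three places and one small table, with no extra charts. The downside is that stated power becomes conditional on chart-confirmation yield and may look less favourable.

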9.6. Data Management

Two major data sources for this study are described in greater detail in various sections throughout the protocol. Their collection, retrieval, preparation, and storage are summarized as follows:

1. **Optum's EHR database:** The EHR Database is a longitudinally linked structured data source. It has been formally de-identified by an independent statistical expert following HIPAA statistical de-identification rules and managed according to Optum customer data use agreements.^{1,2} The EHR includes structured fields rendered by NLP technology, wherein Optum data experts mine provider notes and then normalize, validate, and integrate them into the electronic database.

In addition to these structured data, Optum has clinical notes available from some EHR systems and can use technology to search the verbatim text for phrases of interest and extract a small portion of those notes for review and clinical assessment. All data elements from this source are stored on Optum's firewalled, password-protected database. These data can only be extracted by approved Optum study personnel using standard and commercially available software (eg, SAS, SQL, Python).

2. **Optum's Integrated Claims-Clinical database:** The EHR will be supplementally linked to patients in Optum's Integrated Claims-Clinical adjudicated claims database. For a subset of these patients, electronic clinical notes will undergo manual clinician review to confirm myocarditis cases.

For the validation process using the electronic clinical notes (which will be converted to deidentified structured data for analyses), the Optum Natural Language Programming (NLP) team will determine if clinical notes are available for all qualifying HF patients ≥ 50 years old with a clinical diagnosis of ATTRwt-CM or non-amyloid HF. Optum will perform a series of "enhanced search" queries on the patient notes to determine key term content. Next, the Optum NLP team will use the key terms to extract note snippets into a file for review by the Optum Clinical team. These notes snippets will then be used to validate ATTRwt-CM or non-amyloid HF per Pfizer clinical team specification that were identified in the EHR using the inclusion and exclusion criteria specified in [Section 9.2.1](#) and [Section 9.2.2](#). After clinical review of the notes involving two clinicians from Optum, and categorization of the content for analysis, the resulting table of criteria will be created. The ATTRwt-CM (cases) or non-amyloid HF (controls) will then be classified as validated or not validated, and relevant information entered into a spreadsheet that will serve as the data collection tool. Finally, the Optum clinical review team will provide these results of the case validation to the Pfizer Core Study Team so that the ML algorithm could be run using the structured data to calculate the sensitivity and specificity of the algorithm.

Data will be handled and analyzed using Python software, Version 3.6 or later.

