9.8. Quality Control

All codes and/or code algorithms will be reviewed by the clinical lead from Pfizer, as well as the protocol authors. The study team will be responsible for upholding high levels of quality control throughout the data analysis and reporting processes. Quality control (QC) checks will be performed on all Python programming, data tables, and reports generated in the course of this research. QC findings and documentation of remedial action will be maintained. Storage of programming, data, and reports will be carried out per standard procedures.

In the validation study, after the Optum NLP team creates key term tags for use in the snippet review for the two Optum clinicians who will review patient notes with these key terms mentioned, the two clinicians will record their findings from the notes regarding whether the notes support a ATTRwt-CM or non-amyloid HF. These results will be provided to the Pfizer study team for review and any clarifications or questions will be managed between the two groups until resolved.

PFIZER CONFIDENTIAL

CT24-WI-GL02-RF02 4.0 Non-Interventional Study Protocol Template For Secondary Data Collection Study

01-Jun-2022

Page 20 of 25

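### Section 9.6 describes confirming a provisional case or control status, and the visible text does not say that the chart reviewers are masked to it

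*Combined protocol and SAP*

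**What the plan says.** Section 9.5 starts from two groups: 422 potential ATTRwt-CM records found by keyword search, and a similar number of control charts. Appendix B adds code lists for identifying cases and controls; their content is not visible.

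Section 9.6 describes the review. Key terms are used to search the notes and "extract a small portion of those notes for review and clinical assessment". The snippets serve to validate diagnoses already identified in the EHR. Two clinicians review them, a table of criteria is made, and then: "The ATTRwt-CM (cases) or non-amyloid HF (controls) will then be classified as validated or not validated". Section 9.2 likewise gives the purpose of the manual review as confirming the diagnosis.

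Section 9.8 puts the task differently: "the two clinicians will record their findings from the notes regarding whether the notes support a ATTRwt-CM or non-amyloid HF". That asks which diagnosis the notes support, not whether a given one is upheld.

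No visible section says whether the clinicians know a record's provisional status, whether the two groups are mixed, or whether the two readings are independent. Section 9.1 refers the detailed ascertainment method to Appendix A, which is an embedded file.

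**The concern.** A verdict of validated or not validated needs a label to validate. If the clinicians have that label when they read, an ambiguous snippet (amyloid suspected, work-up ordered, result not shown) may be read toward it. An error made when the record was selected can then survive the step meant to remove it.

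This matters because the study exists to replace codes with a clinical diagnosis. Section 7 concedes that a diagnosis code often reflects screening for the disease and not a confirmed diagnosis. Chart review is the safeguard against that.

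The direction of the bias is not fixed. Label errors unrelated to the model score pull both metrics down. But Section 9.7.1 feeds patients' diagnosis codes to the model, and Appendix B uses code lists to identify cases and controls. Errors that come from coding could therefore agree with the model and push the metrics up.

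**Working it through.** **Inputs.** From Section 9.5: "H0: Sensitivity ≤ 0.80", "H1: Sensitivity ≥ 0.90", "H1: Specificity ≥ 0.82", null specificity 0.72 and margin 0.10. From Section 9.7.1: one-sided alpha 0.05, power 0.90, cut points 0.8561 and 0.7761. The documents give no label error rate after chart review, so every rate below is an assumption.

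**The plan's own figures.** Section 9.5 states: "For 90% power, the formula results in 78 individuals for sensitivity and 128 individuals for specificity". Its formula gives N = (1.645 + 1.282)² × p(1−p) / 0.10².
- Sensitivity, p = 0.90: 77.07, rounded up to 78, as stated.
- Specificity, p = 0.82: 126.40, rounded up to 127, against 128 stated.

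These numbers take the chart label as free of error.

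**Errors unrelated to the score.** Let e be the share of validated cases that are really non-amyloid HF, and f the share of validated controls that are really ATTRwt-CM. A mislabelled case is model-positive with probability 1 − 0.82 = 0.18. A mislabelled control is model-negative with probability 1 − 0.90 = 0.10.
- Observed sensitivity = 0.90(1−e) + 0.18e = 0.90 − 0.72e
- Observed specificity = 0.82(1−f) + 0.10f = 0.82 − 0.72f

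The chance of passing is exact binomial and assumes that success means a one-sided 95% Wald lower bound above the null value.

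| Assumed error | Sensitivity | Pass, n=78 | Pass, n=422 | Specificity | Pass, n=128 | Pass, n=422 |
|---|---|---|---|---|---|---|
| 0% | 0.900 | 0.85 | 1.00 | 0.820 | 0.89 | 1.00 |
| 5% | 0.864 | 0.50 | 0.975 | 0.784 | 0.58 | 0.926 |
| 10% | 0.828 | 0.19 | 0.45 | 0.748 | 0.22 | 0.38 |

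The expected value reaches the plan's cut point at (0.90 − 0.8561)/0.72 = 6.1% error, and the same for specificity. It reaches the null at 0.10/0.72 = 13.9%.

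**Errors that agree with the score.** Take the extreme case in which every mislabelled record matches the model, with the true value at the null and 10% error.
- Sensitivity: 0.80 × 0.90 + 0.10 = 0.82. The chance of a false pass rises from 0.069 to 0.147 at n = 78, and from 0.056 to 0.289 at n = 422.
- Specificity: 0.72 × 0.90 + 0.10 = 0.748. It rises from 0.072 to 0.224 at n = 128, and from 0.055 to 0.378 at n = 422.

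In this direction a larger sample makes a false pass more likely, because it does not remove the bias.

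**The case against.** A reader might infer from Section 9.6 that the clinicians have the presumed answer in front of them. The documents do not say so. The sentence is passive and does not name who classifies. It follows the clinicians' review and a table of criteria, so it could describe a later comparison. Section 9.8, the most direct statement of what the clinicians record, is neutral. Appendix A may specify masking, and its being unreadable here is not a gap in the plan. This stands: what can be said is that masking is not stated in the visible text.

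A reader might also take the table as the cost of unmasked review. It is not. It shows the effect of all label error left after review, whereas masking can remove only the part caused by knowing the status. The 10% control row is also demanding for a disease that the protocol calls rare, and a case that the notes never diagnose would be missed by masked readers too.

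Nor does the plan say that keyword errors are common. Section 7 speaks only of the ICD-10 code, and provisional status may come from keywords, code lists or both.

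There are safeguards. Section 9.6 runs the model after the review, two clinicians take part, and a not-validated verdict can remove false hits. The first hides the model result but not the provisional status. The others help, but do not prevent reading toward a known label.

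**Conclusion.** The point holds as a matter of what the plan leaves unstated. Sections 9.2 and 9.6 describe confirming a provisional status, Section 9.8 describes a more neutral task, and the visible text does not say that reviewers are masked. The passages should be reconciled.

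The stakes can be shown only under assumed error rates. If errors are unrelated to the score, 5% to 10% of wrong labels costs 3.6 to 7.2 percentage points of the affected metric, against a margin of 10. If errors agree with the score, the bias runs upward and the risk of a false pass grows. The share of any such error that unmasked review would cause cannot be estimated from the documents. If Appendix A already masks the reviewers, a sentence in Section 9.6 saying so, with matching wording in 9.8, would settle the point.

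**What to change.** Amend Sections 9.6 and 9.8, and Appendix A if needed, so that:
- candidate case and control records are pooled, searched with one key-term set, put in random order and stripped of candidate status;
- the same two clinicians each independently record ATTRwt-CM, non-amyloid HF or not determinable under Appendix A;
- candidate status is merged back only after both readings are entered.

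This has to be in place before reading starts, because masking cannot be added to charts already read with a label. It needs a change of wording and a shuffled review file. The charts, the reviewers and the required 78 and 128 individuals stay the same. Masking will be imperfect, since a snippet can reveal the work-up that made the record a candidate. A few more records may be read as not determinable; Table 1 has no cell for these, so the amendment should say how they are handled.
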